### 12.1 Subject Disposition

The number of subjects included in each subject set (i.e., Randomised Set, Safety Analysis Set, Full Analysis Set and Immunogenicity Analysis Set) will be summarised by treatment group.

The number and percentage of subjects who prematurely discontinued during the study will be presented by treatment group for Days 1-85 for the primary analysis, and for Days 86-225 in addition for the follow-up analysis. Reasons for premature discontinuation as recorded on the termination page of the eCRF will be summarised (number and percentage) for each treatment group. All subjects who prematurely discontinued will be listed by discontinuation reason for the Randomised Set. In addition, each individual subject's membership of each analysis set will be listed.

### 12.2 Protocol Deviations

Per PRA processes, important protocol deviations data will be entered into our Clinical Trials Management System (CTMS). The study team and Altimmune will conduct on-going reviews of the deviation data from CTMS and the resulting set of evaluable subjects throughout the study, adjusting the 'important' deviation criteria as seems appropriate. The evaluable subjects set (Immunogenicity Analysis Set) must be finalised at the post-freeze data review meeting (or earlier), prior to database lock.

A summary of the number and percentage of subjects with important protocol deviations by treatment group will be produced for the Randomised Set.

All protocol deviation data will be listed for the Randomised Set.

## 12.3 Treatments

### 12.3.1 Extent of Investigational Product Exposure

The total number of injections administered will be presented descriptively, both as continuous data and using the following categories on the Safety Analysis Set:

- Number of injections administered [1,2,3]

In addition, the number of subjects with 1, 2 or 3 injections not fully administered will be summarised. The reasons for any dosing interruptions/incomplete administrations will be included in the data listing.

As investigational product is administered via injection by the site, treatment compliance will not be calculated.

### 12.3.2 Concomitant Medications

Version WHO DDE B2 Mar\_2017 of the WHO Drug Dictionary will be used to classify prior and concomitant medications by preferred term.

Prior medication is defined as any medication with the start date and time prior to the date and time of the first dose of investigational product. All prior medication will be recorded on the appropriate eCRF page.

Concomitant medication refers to all treatments taken at any time from the date and time of the first dose of investigational product through 30 days after the last dose of investigational product. It is possible for a medication to be considered both prior and concomitant. For instance, a medication that begins prior to the first dose of investigational product and continues during the study.

Concomitant medications will be coded to Anatomical Therapeutic Chemical (ATC) group (level 2) and preferred term. For summaries, multiple medication usage by a subject in the same ATC level or preferred term category will be counted only once.

For the Day 85 analysis the following summary will be presented for the Safety Analysis Set by treatment group:

- All concomitant medications by preferred term.

For the Day 225 analysis the following summaries will be presented for the Safety Analysis Set by treatment group:

- Concomitant medications that were started prior to first dose of investigational product and continued after the first dose of investigational product (i.e., medications that are considered both prior and concomitant) by ATC level 2 and preferred term
- Concomitant medications that were started on or after the first dose of investigational product by ATC level 2 and preferred term.

All prior and concomitant medication for individual subjects will be listed.

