7.7 Follow-up assessments

Subjects will be contacted (telephone call) by clinic staff at approximately 4-weekly intervals between Day 85 and Day 225 to check subject health.

Visit 9:

A follow-up visit will be performed at Day 225. The following assessments will be performed:

- HBsAg and HBsAb monitoring
- HBV DNA monitoring
- Vital signs
- Physical examination
- Safety laboratory tests
- Documentation of concomitant medication
- Blood for CMI
- 12-lead ECG
- Documentation of SAEs and AESIs (autoimmune disease and liver flares)

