7.9 Allowed visit intervals

Allowed visit intervals are as follows:

- **screening and randomisation:** subjects must be screened 7 to 28 days (± 2 days) and can be randomised to treatment up to 3 days prior to the first injection.
- **first dose:** Visits 1 and 2 must be done on Days 1 and 2, respectively; Visit 3 may be done within ± 1 day of Day 8
- **second dose:** Visit 4 may be done within 28 days (± 7 days) of Visit 1; subjects must be phoned the day after Visit 4; Visit 5 should be done 7 (± 1 day) days after Visit 4
- **third dose:** Visit 6 may be done 28 days (± 7 days) after Visit 4; subjects must be phoned the day after Visit 6; Visits 7 and 8 should be done 7 (± 1 day) and 28 days (± 1 day) respectively after Visit 6
- **follow-up:** Visit 9 must be done 24 (± 4 weeks) weeks after the last dose (Visit 6)

The scheduled assessments may shift in instances where a visit window is used; subsequent visit dates should be recalculated from the date of the new visit. If a second dose visit is missed, the dose can be given 6 weeks after the first dose and noted as out of window. If the dose is later than 6 weeks, the second dose visit can be skipped and given at Visit 3 at 8 weeks as per schedule to avoid a delay in the schedule.

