8.5 Dosage schedules

Each dose of Vaccine FP-02.2, Vaccine FP-02.2/IC31®, Placebo or IC31® will be administered as an IM injection (1.0mL) in the deltoid muscle, where possible, of the non-dominant arm by appropriately trained clinical staff members. The first dose will be administered on Day 1, the second dose approximately 4 weeks later on Day 29 and the third dose approximately 4 weeks after the second dose on Day 57. Subjects will stay in the unit for at least 4 hours following administration of the first dose and at least 2 hours following administration of the second and third doses.

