10.3 Statistical analysis plan

The proposed statistical analyses for this study will be detailed in a separate statistical analysis plan (SAP), which will be finalised prior to database lock. Any changes to the statistical analysis described in this protocol do not require a protocol amendment but must be described as a 'change to the protocol planned statistical analysis' in the SAP and the clinical study report.

The statistical analysis and report will conform to the relevant ICH requirements.

Data listings and summary tables will be generated using the software SAS® Version 9.3 or later. All data recorded in the eCRFs will be included in data listings. The SAS datasets and programs will be made available to the Sponsor at study closure.

Summary tables and data listings will be presented by treatment arm and time point.

The standard summary statistics for continuous variables will comprise number of valid observations, arithmetic mean, standard deviation, median, quartiles, minimum, and maximum. The geometric mean and coefficient of variation will also be presented for continuous variables which are positive and substantively positively skewed (such as liver enzyme levels, ELISpot counts and measures of viral load). The standard summary statistics for categorical data will comprise absolute and relative frequencies (proportions).

If continuous variables are assessed both at and after baseline, change from baseline will be calculated and summarised. If categorical variables are assessed both at and after baseline, then cross-tabulations will be presented by category at baseline.

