### 10.2 Primary and Follow-up Analyses

After all participants in cohort 3 have completed Day 85, the primary analysis of the safety data collected up to Day 85, immunogenicity (except HLA genotyping) and virology data will be performed. A secondary follow-up analysis of all immunology and safety data, including those collected between Day 86 and Day 225 for all cohorts will be conducted. The Investigators, all site staff, the subjects and trial monitors will remain blinded between the two analyses. Staff at PRA and Altimmune will unblind at the primary analysis at Day 85 of the final participant in cohort 3.

For the primary analysis, the data will be cut at day 85 for each individual subject regardless of their current progress in the study. Adverse events and concomitant medications occurring after day 85 will not be included in the outputs for the primary analysis.

The information from the primary analysis is required to inform the design of the next clinical study and confirm the formulation and dose to use.

This SAP describes the analyses that will be done at both of these time points. The same tables, figures and listings listed in [Appendix 1](#) will be produced at both time points.

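### The concomitant-medication definition closes 30 days after last dose, so a drug first started later appears in none of the planned medication tables, including the Day 225 tables

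*SAP*

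**What the plan says.** SAP 12.3.2 uses two classes. For the first: "Prior medication is defined as any medication with the start date and time prior to the date and time of the first dose". The second, concomitant medication, covers any treatment taken from first dose "through 30 days after the last dose of investigational product". A drug may be in both classes.

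All three planned summaries are of concomitant medications. Table 14.1.4.1 is assigned to the Day 85 analysis. Tables 14.1.4.2 (begun before first dose) and 14.1.4.3 (begun at or after first dose) are assigned to the Day 225 analysis. The listing sentence in SAP 12.3.2 and the title of Listing 16.2.4.6 also name only prior and concomitant medication.

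Other sections look further ahead:
- Protocol 7.7: "A follow-up visit will be performed at Day 225", and its task list includes "Documentation of concomitant medication".
- Protocol 8.9 requires every treatment to be entered in the eCRF.
- Protocol 10.9.7 calls for a medication summary by arm and sets no time limit.
- Protocol 10.3: "All data recorded in the eCRFs will be included in data listings".
- SAP 10.2 plans a follow-up analysis of immunology and safety data, "including those collected between Day 86 and Day 225 for all cohorts will be conducted". It leaves medications after Day 85 out of the primary outputs only.
- SAP 12.6.1 uses the same 30-day limit for treatment-emergent events, but exempts SAEs and AESIs, all of which are summarised.
- SAP 4.1 declares two changes from the protocol. Neither concerns medications.

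**The concern.** The two definitions do not cover the whole study. A drug first started more than 30 days after last dose is not prior, and the SAP's own wording makes it not concomitant. It has no row in any medication table, and the tables planned for Day 225 can hardly differ in content from what was available at Day 85.

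What is at stake is the reading of late safety data. SAEs and AESIs through 6 months after last dose are primary variables (Protocol 3.3.1, SAP 7.1), and the AESIs are hepatic flares and autoimmune conditions. HBsAg, HBV DNA and PBMC samples are also taken at Day 225. A steroid or interferon course, a hepatotoxic drug, or treatment begun for a late AESI would bear on how those data are read. Exclusion criteria 4 and 13 in Protocol 6.2 already treat several such drugs as affecting the immune system. As planned, the late event is tabulated by arm, while a drug newly started before or because of it is not. With about 10 subjects per arm, one or two such drugs could matter to a reader.

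**Working it through.** **Inputs**
- Last scheduled dose: Protocol 8.5 places the "third dose approximately 4 weeks after the second dose on Day 57".
- Window length: 30 days after last dose (SAP 12.3.2).
- Visit 9: 24 weeks after last dose, with a window of 4 weeks either way (Protocol 7.9).
- Earlier scheduled doses: Day 1 and Day 29.
- Primary cut: Day 85 (SAP 10.2).

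**Step 1. Reproduce the plan's own figure.** 57 + 24 × 7 = 225, which matches the stated Day 225.

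**Step 2. Close of the window for a fully dosed subject.** 57 + 30 = Day 87. The follow-up analysis can therefore add only drugs newly started on Days 86 and 87.

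**Step 3. Uncovered time, for newly started drugs.** Formula: (days from last dose to Visit 9 − 30) / (days from last dose to Visit 9).

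| Visit 9 timing | Days after last dose | Uncovered | Share |
|---|---|---|---|
| 20 weeks | 140 | 110 | 78.6% |
| 24 weeks | 168 | 138 | 82.1% |
| 28 weeks | 196 | 166 | 84.7% |

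**Step 4. Sensitivity to the denominator.** Against the Day 85 to Day 225 phase alone: 138 / (225 − 85) = 138/140 = 98.6%. Against all time from first dose: 138 / (225 − 1) = 138/224 = 61.6%.

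**Step 5. Subjects who stop dosing but stay in the study.**
- One dose: 1 + 30 = Day 31. Uncovered to Day 85: 85 − 31 = 54 of 84 days (64%).
- Two doses on schedule: 29 + 30 = Day 59. Uncovered to Day 85: 85 − 59 = 26 of 56 days (46%).

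Protocol 7.10 encourages such subjects to remain in follow-up, and one injection is enough for the Safety Analysis Set, so the case can arise.

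**Step 6. Follow one drug through the outputs.** Take a drug first started on Day 120 in a fully dosed subject. It starts after first dose, so it is not prior. It starts after Day 87, so it is not concomitant. Tables 14.1.4.1 to 14.1.4.3 are all restricted to concomitant medication, so it enters none of them. A drug started on Day 60 and still taken on Day 120 was taken inside the window and is counted.

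**The case against.** The 30-day window matches the treatment-emergent window in SAP 12.6.1, so tying concomitant medication to that period is a defensible choice. That would carry more weight if the SAP had not also planned Day 225 medication tables, left medications after Day 85 out of the primary outputs only, and exempted SAEs and AESIs from the same limit. The choice is not carried through.

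Several stronger readings are tempting, and the documents do not support them:
- *Late drugs vanish from the listing as well.* The SAP wording is narrow, but it does not say that other recorded drugs are removed. Protocol 10.3 requires all eCRF data to be listed, SAP 4.0 says the SAP is to be read with the protocol, and SAP 4.1 declares no narrowing. This is a conflict of wording, not an established loss.
- *82% of follow-up medication goes unreported.* The figure is a share of calendar days, not of medication records, and it applies only to drugs newly started in that stretch. Background entecavir or tenofovir continued from before entry is still counted.
- *A late change of antiviral could not be seen by arm.* Protocol 10.8.1 separately calls for NUC exposure to be tabulated, and SAP 4.1 does not withdraw this. SAP 12.3.1 and Appendix 1 provide exposure output for investigational product only, but that is a separate gap.
- *Early stopping opens a large hole in the primary analysis.* The documents give no discontinuation rate. A subject who skips the second dose but is dosed at week 8 keeps a window closing near Day 87. Eligible subjects withdrawn before a second dose are replaced (Protocol 7.10.4), although they stay in the Safety Analysis Set.

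It is also fair that every endpoint is descriptive (SAP 12.0), that follow-up immunology is exploratory (Protocol 3.3.2), and that no analysis set or imputation rule is stated to draw on the medication tables. Finally, the flow charts as extracted show no medication mark at Day 225. The extraction may be at fault and Protocol 7.7 is explicit, so this carries little weight.

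**Conclusion.** The point holds for the summary tables. Under the SAP's definitions, a drug first started more than 30 days after last dose has no class and no table, and the Day 225 medication tables therefore omit most of what they were planned to show. Individual records in a listing would not replace a summary by arm.

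The main figure, 138 of 168 days, assumes three doses on schedule and Visit 9 at its nominal date. The early-stopping figures are conditional on subjects stopping and staying in the study. The whole point assumes that medication is recorded at Visit 9 as Protocol 7.7 requires.

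For the listing, the supported conclusion is only that the SAP and Protocol 10.3 disagree in wording and need reconciling.

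Severity is minor to moderate. The tables give descriptive context for late SAEs and AESIs, which are primary variables, but no planned estimate changes.

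**What to change.** In SAP 12.3.2, choose one of two repairs for the tables:
- extend concomitant medication to any treatment taken from first dose to the subject's last study contact, cut at Day 85 for the primary analysis and at Day 225 for follow-up; or
- keep the 30-day window and add a flagged post-treatment category, shown by arm, for drugs first started more than 30 days after last dose.

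The second keeps the match with the treatment-emergent period while still showing the late drugs. In either case, state that Listing 16.2.4.6 holds every recorded medication whatever its class, which settles the conflict with Protocol 10.3.

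The cost is one definition, one sentence on the listing and a slightly longer follow-up table. No new data are needed beyond what Protocol 7.7 and 8.9 already require.

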## 12.4 Demographic and Baseline Characteristics

### 12.4.1 Assessments at Screening only

#### 12.4.1.1 Screening Information

Screening information for each subject screened will be listed, including the dates of screening and enrolment and whether study entry criteria were met.

As per protocol, if a subject is screened and not dosed within the required time-window, that subject may be re-screened. In the event of a subject being re-screened, they will be assigned a new subject number.

Whether or not a subject is a re-screen, and their previously used subject number under their initial screen will be included in screening listings.

#### 12.4.1.2 Fibroscan

A Fibroscan will be performed at screening only to assess for evidence of Liver cirrhosis (Liver cirrhosis is defined as a Fibroscan measurement of >11.5 KPa). Individual subject results will be listed for all subjects screened.

#### 12.4.1.3 Alcohol and Drug Screen

A urine dipstick test for drug abuse and alcohol screen will be performed at screening only. Individual subject results will be listed for all subjects screened.

#### 12.4.1.4 Test for HIV, HDV and HCV

A test for the presence of Human Immunodeficiency Virus (HIV), Hepatitis D Virus (HDV) and Hepatitis C Virus (HCV) will be performed at screening only. Individual subject results will be listed for all subjects screened.

### 12.4.2 Demographics

Descriptive summaries of demographic and baseline characteristics will be presented by treatment group for the Safety Analysis Set. Demographic tables will be repeated for the Full Analysis Set and Immunogenicity Analysis Set.

Subject demographics including age, sex, race, country (at the time of the study), ethnicity, weight, height, and body mass index (BMI) will be summarised for the Safety Analysis Set. Continuous variables will be summarised by descriptive statistics including number of subjects, mean, standard deviation, median, quartiles, minimum, and maximum. Categorical variables will be summarised by the number of subjects in each category and the percentage of subjects out of the total in the respective analysis set.

Height and weight at screening will be used to calculate BMI using the formula below:

$$\text{BMI} = \text{Weight [kg]} / \text{Height [m]}^2.$$

A listing will be created to show all the demographics and baseline characteristics for each subject in the Randomised Set.

Medical history will be presented by system organ class (SOC) and preferred term for the Safety Analysis Set and listed for individual subjects in the Randomised Set. Medical history will be coded using MedDRA version 20.0 preferred terms.

### 12.5 Efficacy Analyses

No efficacy analyses will be performed for this study.

### 12.6 Safety Analyses

All safety analyses will be performed using the Safety Analysis Set unless specified otherwise.

The summary tables by visit will show assessments up to and including Day 85 for the main analysis up to and including the Day 225 follow-up assessments for the follow-up analysis. In the summaries by visit, data will be summarised by scheduled visit as collected in the eCRF. In addition, a "Final visit" will be used for summaries by time point. This visit will consist of the final on-treatment assessment, either the last visit in the study, or the last visit before termination. Unscheduled visits will be displayed in the individual subject data listings only.

#### 12.6.1 Adverse Events

Adverse events will be coded using Version 20.0 or newer of MedDRA.

Treatment-emergent adverse events (TEAEs) are those which first occur or increase in severity or relationship probability to investigational product after the first dose of investigational product through 30 days after last dose of investigational product. Note that SAEs and AESIs are collected through 6 months after last dose of investigational product; therefore, all SAEs and AESIs will be summarized, not just treatment-emergent events.

All AEs which change in severity or relationship to investigational product are assigned a new start date and captured as a new record.

If more than 1 AE with the same preferred term is reported before the date of the dose of investigational product, then the AE with the greatest severity will be used as the benchmark for comparison to the AEs occurring during the study under the preferred term.

An overall summary of TEAEs, including the number and percentage of subjects who experience, and absolute count of treatment-emergent events for:

- Any TEAE
- Any TEAE by maximum severity
- Any TEAE considered possibly related to investigational product (defined as CRF response of "Reasonable Possibility")
- Any TEAE considered possibly related to investigational product by maximum severity
- Any SAEs
- Any SAEs considered possibly related to investigational product
- Any AEs with outcome of death
- Any AESIs (Hepatic flares and autoimmune conditions)
- Any TEAE leading to discontinuation of investigational product

The number and percentage of subjects reporting TEAEs, SAEs, or AESIs will be tabulated in the following ways by treatment group.

- By SOC and preferred term (including absolute count of events).
- By SOC, preferred term and maximum severity.
- By SOC and preferred term for TEAEs possibly related to investigational product in the opinion of the investigator (including absolute count of events).
- By SOC and preferred term for SAEs (including absolute count of events).
- By SOC and preferred term for possibly related SAEs (including absolute count of events).
- By SOC and preferred term for TEAEs leading to discontinuation of investigational product (including absolute count of events).
- By SOC and preferred term for AEs with fatal outcome (including absolute count of events).
- By SOC and preferred term for AESIs (including absolute count of events).

Adverse events of special interest will be identified from the existing study AEs by medical review prior to database lock.

All AEs will be listed by subject. Separate listings will be provided for SAEs, AEs related to investigational product, AEs leading to discontinuation of investigational product, AEs with fatal outcome and suspected unexpected SAEs.

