7.10 Withdrawal criteria

Participation in the study is strictly voluntary. A subject has the right to withdraw from the study at any time and for any reason. If he/she chooses to withdraw, the Investigator must be informed immediately. The Investigator has the right to terminate participation of any subject at any time if the Investigator deems it in the subject's best interest. The reason and circumstances for premature discontinuation will be documented in the subject's eCRF.

In general, all subjects should be encouraged to continue follow up until the end of the study even if they are withdrawn from continued study treatment, to allow collection of late safety data as well as immunogenicity and virology data.

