7.10.1 Possible reasons for discontinuing subjects from continued study treatment

Examples of possible reasons for premature withdrawal of subjects:

- Major protocol violations;
- Pregnancy;
- Serious intercurrent illness;
- AEs which, in the judgement of the PI or Co-Investigator and subject to discussion with the Sponsor's medical advisor, justifies discontinuation;
- Non-compliance with study requirements;
- Withdrawal of consent by the subject;
- Subjects experiencing clinically significant injection site reactions or clinically significant changes in haematology and serum biochemistry results, considered possibly related to administration of the IMP, after a dose may not receive the subsequent dose of medication, at the discretion of the PI, in discussion with the Chief Investigator (CI) or the Sponsor's medical advisor. However, safety, virology and immunogenicity data will continue to be collected until the end of the study unless the subject withdraws his/her consent.

If a subject is withdrawn from study treatment, relevant study procedures e.g. physical examination, clinical laboratory analyses for safety and immunogenicity will be performed wherever possible. The reason(s) for discontinuation will be recorded in the appropriate section of the eCRF. Any subject who prematurely terminates participation and who has received at least one injection of the study treatment will undergo relevant post-study procedures for reasons of medical prudence, including a final examination and safety laboratory studies, unless the subject has withdrawn his/her consent and refuses to be examined and/or have blood drawn.

If a subject terminates participation due to an AE possibly related to the study medication or study procedures, the subject should be followed up by additional examinations according to the medical judgment of the Investigator until the abnormal condition is resolved or the Investigator deems further observations or examinations to be no longer medically indicated. If the subject refuses to be followed up the Investigator should explain the importance of the follow-up and encourage the subject to allow follow up. Subjects who elect to discontinue dosing should be encouraged to continue with other study procedures until the end of study if they are willing.

Study stopping rules

Individual subjects

An individual subject will have treatment discontinued if he/she experiences any one or more of the following events:

- ALT \geq 10 times the ULN

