7.10.4 Replacement of subjects

Eligible subjects who are randomised and withdrawn before their second dose of IMP will be replaced. Subjects who have received two doses of IMP who are subsequently withdrawn from the study will not be replaced.

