9.2 Operational definitions for (S)AEs

The occurrence of AEs will be assessed by non-directive questioning of the subject at each visit. Additionally, AEs volunteered by the subject during or between visits or detected through observation, physical examination, laboratory test or other assessments will be documented. Subjects will be instructed that they must immediately report any AEs, subjective complaints or objective changes in their well-being to the Investigator or the clinic personnel, regardless of the perceived relationship between event and test product.

All AEs must be fully recorded throughout the entire study period (from Screening Visit to Day 85) and will be entered into the subjects' eCRF, whether or not they are considered to be drug-related. Each AE should be described in detail: onset time and date, offset time and date, description of event, severity, relationship, action taken and outcome. From Day 85 and Day 225 only SAEs and AESIs will be collected.

Adverse events should be followed until recovery to the normal state has been achieved. In the event of a subject not returning to the clinical unit, every attempt will be made to contact the subject up to Day 85 after which the outcome of this event will be recorded as lost at follow-up.

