10.9.2 Adverse Events

Adverse events shall be coded according to the current version of MedDRA.

The subject incidence, severity, duration, relatedness and outcome of all treatment emergent AEs will be tabulated by treatment arm, system organ class and preferred term. Separate tables will be provided for fatal events, events leading to withdrawal, serious events and SUSARs.

Treatment emergent AEs will be flagged in the subject data listings.

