## 7.0 Study Variables and Covariates

### 7.1 Primary Variables

- Solicited adverse events (AEs) related to injection site tolerability during the week following each vaccine administration.
- Unsolicited AEs through day 85
- Serious adverse events (SAEs) and AEs of special interest (AESIs) through 6 months after last vaccine dose
- Vital signs
- ECGs
- Safety laboratory assessments including laboratory assessment of liver inflammation and function

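### SAP 12.6.1 closes the TEAE tables 30 days after the last dose, which for subjects who stop dosing early falls short of the Day 85 end of the primary AE variable; SAP 10.2 also leaves its 'day 85' cut undefined

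*SAP*

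**What the plan says.** **The variable and its collection.** Protocol 3.3.1 and SAP 7.1 list as a primary variable "Unsolicited AEs through day 85", with no condition on doses received. Protocol 9.2 has all AEs recorded from screening to Day 85, and only SAEs and AESIs after that. Subjects who stop dosing are meant to stay: under protocol 7.10, "all subjects should be encouraged to continue follow up until the end of the study even if they are withdrawn from continued study treatment". Protocol 7.10.1 adds, for subjects stopped because of injection site reactions or laboratory changes, that "safety, virology and immunogenicity data will continue to be collected until the end of the study unless the subject withdraws his/her consent". One injection is enough to enter the Safety Analysis Set (SAP 9.2).

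**The tabulation.** Protocol 10.9.2 states: "The subject incidence, severity, duration, relatedness and outcome of all treatment emergent AEs will be tabulated by treatment arm". It does not define 'treatment emergent'. SAP 12.6.1 does: the event must first occur, or increase in severity or relatedness, "after the first dose of investigational product through 30 days after last dose of investigational product". It then makes an exception: "all SAEs and AESIs will be summarized, not just treatment-emergent events". Fatal events are also tabulated without the TEAE restriction, and all AEs are listed by subject.

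**The cut.** SAP 10.2 cuts each subject's data at 'day 85' for the primary analysis and leaves later AEs and concomitant medications out of its outputs. SAP 8.2 counts relative day from the first dose. Protocol section 4 uses Day 85 for the visit 28 days after the last injection. Visit dates are recalculated from the actual date of the preceding visit (protocol 7.9, SAP 8.3).

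**The concern.** The primary variable ends at a fixed study day, but the tabulation window ends at a point that moves with each subject's last dose. The two agree for a subject who completes dosing on schedule. They separate for a subject who stops after dose 1 or 2, and protocol 7.10.1 gives AEs, injection site reactions and laboratory changes among the reasons for stopping. The affected subjects may therefore be informative about tolerability. The same definition is used at both analyses, so the later analysis does not restore the missing events to an incidence table.

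The Day 85 analysis is to inform the next study and confirm formulation and dose (protocol 10.11). It is descriptive, with about 10 subjects per arm, so one subject can visibly change a row.

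The undefined cut is a separate problem. Two programmers could follow SAP 10.2 faithfully and produce different primary AE tables from the same data.

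**Working it through.** **Inputs.** Doses on Days 1, 29 and 57. Dose 2 is 28 ± 7 days after dose 1, or at 6 weeks if the visit was missed; dose 3 is 28 ± 7 days after dose 2; Visit 8 is 28 ± 1 days after dose 3 (protocol 7.9, SAP 8.3). The TEAE window ends at last dose + 30 (SAP 12.6.1). About 10 subjects per arm (protocol 10.2).

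**Planned schedule.** 57 + 28 = Day 85, so the nominal visit day reproduces.

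**Days to relative Day 85 outside the TEAE tables** = 85 − (day of last dose + 30), or zero if negative.

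| Last dose received | Window ends | Days untabulated |
|---|---|---|
| Dose 1, Day 1 | Day 31 | 54 |
| Dose 2, Day 22 (earliest in window) | Day 52 | 33 |
| Dose 2, Day 29 (on schedule) | Day 59 | 26 |
| Dose 2, Day 36 (latest in window) | Day 66 | 19 |
| Dose 2, Day 43 (6 weeks) | Day 73 | 12 |
| Dose 3, Day 57 (on schedule) | Day 87 | 0 |

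For any three-dose subject, Visit 8 falls at most 29 days after dose 3, so the 30-day window always covers it. On a relative-day reading, three doses at the earliest windows (dose 3 on Day 43) give a window end of Day 73, which is past Visit 8 (Days 70 to 72) but 12 days short of relative Day 85.

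**Share of AE follow-up days untabulated.** The documents give no stopping rate. Assume that 1 to 3 subjects in an arm of 10 stop early and stay in follow-up. The arm contributes 10 × 85 = 850 days.

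- Lowest: one subject whose last dose is dose 2 at week 6: 12/850 = 1.4%.
- Highest: three dose 1 stoppers, not replaced: 3 × 54 = 162; 162/850 = 19.1%.
- Protocol 7.10.4 says: "Eligible subjects who are randomised and withdrawn before their second dose of IMP will be replaced". If all three are replaced, the arm has 13 × 85 = 1105 days and the share is 162/1105 = 14.7%.
- If subjects withdrawn before dose 2 leave the study altogether, only dose 2 stoppers count: 12/850 = 1.4% to 3 × 33 = 99, 99/850 = 11.6%.

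**One subject in a table row.** 1/10 = 10 percentage points, or 1/13 = 7.7 with three replacements. Subjects are counted once per row, so this is a maximum: it applies only where that subject has no earlier TEAE in the row.

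**The cut.** In window, dose 2 falls on Days 22 to 36 and dose 3 on Days 43 to 71. Visit 8 therefore falls between 43 + 27 = Day 70 and 71 + 29 = Day 100.

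- Cut at relative Day 85: as few as 85 − 71 = 14 days after an in-window dose 3 enter the primary analysis. With dose 2 on Day 43, dose 3 can be as late as Day 78, leaving 85 − 78 = 7 days.
- Cut at Visit 8: nothing up to Visit 8 is lost, but SAEs and AESIs on up to 85 − 70 = 15 days (Days 71 to 85) after an early Visit 8 fall outside the primary analysis.

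**The case against.** **A reader might infer that the SAP shortens a window set by the protocol.** The documents do not support that. Protocol 10.9.2 leaves 'treatment emergent' undefined, and protocol 10.3 sends analysis detail to the SAP, so SAP 12.6.1 fills a gap. A 30-day limit is a design choice with a reason behind it: the alternative counts events up to 84 days after a single dose. What remains is a mismatch with the SAP's own primary variable in 7.1.

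**A reader might infer that late liver signals in early stoppers disappear.** They do not. By-visit laboratory and vital-sign tables run to Day 85 with no TEAE limit (SAP 12.6, 12.6.3, 12.6.4). Clinically significant post-baseline laboratory values are tabulated. Hepatic flares are AESIs and are summarised regardless of timing. Solicited reactions concern only the week after each dose. The Safety Review Committee works from database listings (SAP 10.1), so its decisions are untouched. This part of the objection stands and limits the concern to non-serious, non-AESI, non-fatal events.

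**On the cut,** SAP 8.2 defines relative day for events, which makes that the natural reading for dated AEs, and whatever is excluded reappears in the Day 225 analysis. The exclusion is a delay, not a loss. But SAP 10.2 does not refer to 8.2, and in the same paragraphs it also uses Day 85 for a completed visit.

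**A reader might also infer that an ECG result is compromised,** because ECG is a primary variable and the objective is set at Day 85. ECG is scheduled only at screening and Visit 9, but SAP 12.6.5 already ties the shift to follow-up, and the primary list gives ECG no Day 85 time point. No result changes.

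**Conclusion.** The mismatch is real. For subjects who stop after dose 1 or 2 and stay in follow-up, the plan leaves part of its own primary AE variable out of every incidence table: 54 days after one dose, 26 after two on schedule (19 to 33 in window, 12 if dose 2 is at week 6). The direction is always towards undercounting.

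The size is unknown. The range of about 1.4% to 19% of AE follow-up days rests on an assumed 1 to 3 stoppers per arm of 10, and a share of days is not a share of events. The top of the range also needs all three to stop after dose 1, remain in follow-up and not be replaced. With no early stoppers the loss is zero when Day 85 means Visit 8; on the relative-day reading, three-dose subjects with early windows are also affected, by up to 12 days.

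The undefined cut is a smaller but genuine ambiguity, since it can reduce follow-up after an in-window dose 3 to 14 days in the primary analysis. Both points are worth correcting before database lock because correction is cheap. Neither undermines the serious-event or liver monitoring outputs.

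**What to change.** 1. In SAP 12.6.1, tabulate AEs from first dose through the latest of Visit 8, relative Day 85 and last dose + 30 days, for every dosed subject whenever dosing stopped, and within the data cut at the primary analysis. Keep the 30-day flag in the listing so that the narrower view stays available. Note this in SAP 4.1.
2. In SAP 10.2, define the AE and concomitant-medication cut as the later of Visit 8 and relative Day 85. Use the same meaning of 'day 85' in SAP 7.1.
3. Housekeeping only: note that ECG and HBV DNA have no scheduled post-dose data before Day 225, so their shift or change outputs belong to the Day 225 analysis, although SAP 10.2 asks for the same outputs at both. The objectives need no rewriting.

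**Cost.** Wording in a few SAP sections and a small programming change; no new visits or samples. Tabulated AE counts may rise slightly and will include events remote from the last dose. The cut will vary by subject, from Day 85 to Day 100 in window (Day 107 if dose 2 is given at week 6). The ECG and HBV DNA note adds no data.
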